4.1 General considerations

All results are based on the FAS.

4.1.1 Data presentation

No formal hypothesis test will be applied in the study. The data will be presented descriptive where 95 % confidence intervals will be presented.

Numerical data will be presented in summary tables by number of patients, arithmetic mean, median, standard deviation (SD), minimum and maximum. Categorical data will be presented by number and percent of patients as well as number events (where applicable).

Summary tables will in general be presented by treatment and total unless this is not appropriate for specific tables.

All data will be listed by patient.

4.1.2 Baseline definition

Baseline value is defined as the baseline value in the feeder trial. Change from baseline will be calculated for patients with relevant endpoints, and for these the baseline value is defined as the baseline value in the feeder trial. Change will be calculated as the difference between post values for a given timepoint and baseline values (post value to a timepoint minus baseline value). If the post value or baseline value are missing, then the change from baseline will also be missing.

4.1.3 Multiplicity

The study is descriptive, so no correction for multiple testing will be done.

4.1.4 Data imputation

In general, missing data will remain as missing and the missing values will not be adjusted. There are some expectations described below.

Adverse events

Missing values will be treated as missing except for causality, toxicity, intensity, seriousness and outcome of an AE, in which case a “worst case” approach will be taken. If causality is missing, it will be set to “related”. If intensity is missing, it will be set to “severe”. If seriousness is missing, it will be considered as a Serious Adverse Event (SAE). If outcome is missing and no date is given for the outcome it will set to “not yet recovered”.

Dates for adverse event and concomitant medical

Missing or partial start dates for adverse events and concomitant medication data will be handled in the following way:

- If the start date is totally missing, the date will still be missing.

- If the start day is partial where only the year are given, then the two cases are considered:
 - If the available partial date (year) is equal to or after the year of treatment start date, then the start date will be imputed as start of the year (1st January YYYY) (if the year is not same as that of the treatment start date) or treatment start date (if the year is same as the treatment start date).
 - For the partial end dates will similar procedure be used as for the start dates. The only difference is the imputation for missing days. Missing days is imputed to the end of the month instead of the start of the month. It will be checked that the imputed end dates fall after the corresponding start dates.

4.2 Patient disposition

All patients screened will be accounted for. The number of patients in the analysis set and the number of patients who completed the trial will be summarized by treatment group. Furthermore, the number of patients who withdraw from the trial will be summarised overall and by treatment group and reason for withdrawal. Patients screened but not found eligible will be listed with reason(s) for screening failure.

4.3 Demographics and other baseline characteristics

4.3.1 Patient Characteristics

Data from the clinical assessments will be summarised or listed by treatment group and each time point using descriptive techniques. Summary statistics (n, arithmetic mean, standard deviation, median, minimum and maximum values) will be presented for continuous variables (absolute values at each time point and, if relevant, changes from baseline) and counts and, if relevant, percentages will be presented for categorical variables. Where appropriate, the presentation of results will include confidence intervals of estimated treatment differences and plots.

4.3.2 Demographics and Other Baseline Characteristics

The following demographic variables will be summarised by treatment group: Age, sex, race, height, weight and Body Mass Index (BMI). The demographics variables will additionally be listed by patient.

Previous kidney transplant history will be presented in a summary table by treatment group and listed by patient. The donor type (living or deceasing) will be listed by patient.

4.3.3 Recent and Concomitant Medication

Recent and concomitant immunosuppression medication will be summarised by anatomical therapeutic chemical (ATC) code and generic drug name for each treatment group.

4.4 Efficacy

Data is for the patients included in 20-HMedIdeS-18 and will be presented by treatment group.

4.4.1 Primary efficacy analysis

Overall graft survival at Year 3. Graft survival is defined as time from start of treatment (imlifidase or plasma exchange) of active or chronic active AMR in feeder trial to graft loss. Graft loss is defined as permanent return to dialysis for at least 6 weeks, re-transplantation, or nephrectomy. If dialysis is used to define graft loss, the date of graft loss will be the first day of the last ongoing dialysis period reported.

The primary endpoint, overall graft survival at Year 3, will be analysed by the Kaplan-Meier survival method. The overall graft survival will be tabulated and presented graphically by treatment.

The following events will be censored at the time of occurrence: withdrawal from the trial without graft loss, evaluation time point and end of trial without graft loss.

The reason for graft loss will be tabulated by time.

4.4.2 Secondary efficacy analyses

4.4.2.1 Graft survival at Year 1 and 2

Graft survival at Year 1 and Year 2 will be listed by patient and summarized by treatment and time point and analysed using the same methods as for the primary efficacy analysis .

4.4.2.2 Patient survival

Patient survival, defined as time from start of treatment in feeder trial to death, evaluated at Year 3 will be listed by patient, summarized by treatment, and analysed by the Kaplan-Meier survival method. The patient survival will be tabulated and presented graphically by treatment.

4.4.2.3 Kidney function

Kidney function is evaluated by estimated Glomerular Filtration Rate (eGFR), S/P-creatinine and albumin/creatinine ratio in urine at 1, 2, and 3 years after start of treatment in feeder trial.

The eGFR will be calculated as a part of ADaM programming, using the Modification of Diet in Renal Disease Study (MDRD) equation (2):

$$\text{eGFR (mL/min/1.73 m}^2\text{)} = 175 \times (\text{Cr})^{-1.154} \times (\text{Age})^{-0.203} \times (0.742 \text{ if female}) \times (1.212 \text{ if African American}),$$

where Cr stands for creatinine value and Age are measured in years at the visit date. This formula assumes that Cr is given in the mg/dL unit.

Variables will be listed by patient and summarized by treatment at Year 1, 2, and 3 after start of treatment in feeder trial.

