Imlifidase is an IgG-degrading enzyme of *Streptococcus pyogenes* that cleaves all four human subclasses of IgG with high efficacy and strict specificity. Cleavage of IgG generates one F(ab')₂- and one homodimeric Fc-fragment and efficiently neutralizes Fc-mediated activities of IgG, including complement activation and Fcγ receptor binding. The rapidity of the IgG cleavage by imlifidase is considered a major advantage as compared with plasma exchange, which often requires several rounds over several days to achieve a sufficient DSA reduction. Within a few hours after dosing, the entire pool of IgG is fully cleaved into F(ab')₂ and Fc fragments thereby creating a window where IgG levels are kept very low for approximately one week. Previous clinical trials supporting the rapid elimination of anti-HLA antibodies by imlifidase are summarized in [Table 1](#).

The short-term efficacy and safety of imlifidase in active and chronic active AMR is currently being investigated in an ongoing randomized, open-label, multi-centre trial, using plasma exchange as active control (16-HMedIdeS-12). A total of 30 subjects will be included, 20 in the imlifidase arm and 10 in the plasma exchange arm. In brief, the primary objective is to investigate the efficacy of imlifidase in removing DSA in patients who are experiencing an

AMR episode after kidney transplantation. Key efficacy outcome measures such as kidney function and graft survival will be followed as secondary endpoints, as will DSA levels, up to 180 days after treatment.

While a rapid removal of DSA by imlifidase might be expected, DSA is likely to rebound unless well-controlled by concomitant immunosuppressive therapy. Therefore, there is a need to also address the long-term benefit of imlifidase in AMR.

Table 1. Summary table of clinical studies with imlifidase showing rapid effect on anti-HLA antibodies/DSA.

| Trial No. / EudraCT No./ IND No. | Phase / Subjects | Main objectives |
|--|--------------------------------------|---|
| 13-HMedIdeS-02 / 2013-005417-13 | II / Patients with CKD N= 8 | Efficacy in patients with CKD defined as imlifidase dosing scheme resulting in HLA antibody levels acceptable for transplantation, within 24 h from dosing. Safety in the transplantation setting. |
| 13-HMedIdeS-03 / 2014-000712-34 | II / Patients N=10 | Safety in the transplantation setting. Efficacy defined as HLA antibody levels acceptable for transplantation. |

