3. INVESTIGATIONAL PLAN

3.1 Overall Trial Design

This is an observational 3-year follow up trial. Trial sites that have participated, or are currently participating, in trial 16-HMedIdeS-12 (the “feeder trial”) will be contacted and requested to approach subjects for enrolment in the trial. Up to 30 subjects will be included depending on subjects’ willingness to participate in the trial. Subjects who lose their graft during the feeder trial or in the intermediate time before being able to enter this trial will not continue in the trial but information about the graft loss will be collected.

The trial will primarily evaluate graft survival. The subjects will attend 3 follow up visits 1, 2 and 3 years after start of treatment in the feeder trial. Signing of Informed Consent may be performed any time between last visit in the feeder trial and up to first visit in the follow up trial.

Kidney function and patient survival will be assessed. Graft rejection episodes will be determined using classification according to Banff 2017 or later version. Information from kidney biopsies performed within standard of care will be collected. Blood samples for analysis of DSA and ADA will be collected at each visit. Medically relevant comorbidity (infections, malignancy, diabetes mellitus, cardiovascular events and comorbidity leading to worsening of kidney function), will be recorded. Information about treatments of graft rejection episodes will be recorded (e.g. plasma exchange and IVIg) as well as creatinine-level and DSA data conducted within standard of care due to the graft rejection episode.

If a planned visit cannot be performed, subjects may be contacted by phone and assessments described in this protocol may be collected from a local laboratory.

The overall trial outline is summarized in [Figure 1](#).

Figure 1. Overall trial design.

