3.2 Trial Schedule

The first subject first visit is planned in October 2020, 1 year after first subject was treated in the feeder trial.

Last subject last visit in this trial will be 3 years (+/- 4 months) after last subject's first visit in the feeder trial.

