6.1.1 Screening

Screening may be conducted at the earliest at the last visit in feeder trial and at the latest at Year 1 (one year after start of treatment in feeder trial +/- the visit window of 2 months).

The following assessments and activities will be performed:

- Check inclusion and exclusion criteria
- Sign informed consent, see section 15.5
- Assessment of graft survival. For subjects with graft loss after last visit in the feeder trial, date, reason for graft loss, medical history, and root cause will be recorded.
- Record patient survival (if applicable, date and cause of death)

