6.1.2 Year 1, Year 2, and Year 3 (End-of-Trial)

The following visit windows applies:

Year 1: (+/- 2 months)

Year 2 and Year 3 (End-of-Trial): (+/- 4 months)

The following activities and assessments will be performed:

- Assessment of graft survival. For subjects with graft loss since last visit in the feeder trial or screening (if screening is done at a separate visit), date, reason for graft loss, medical history, and root cause will be recorded.
- Record patient survival (if applicable, date and cause of death)
- Collect information about graft rejection episodes, (classified by Banff 2017 or later). For-cause biopsies together with contemporaneous local DSA analyses, kidney function parameters (P-creatinine, U-albumin/creatinine ratio) and treatments (e.g. plasma exchange and IVIg) will be collected to assess the rejection episodes.
- Record information from standard of care biopsies, if available
- Sample for S/P-creatinine will be drawn (eGFR will be calculated by the Sponsor)
- Collect urine sample for measurement of albumin/creatinine ratio
- Sample for HLA antibodies, including DSA, and ADA will be drawn
- Record comorbidity such as infections, malignancy, diabetes mellitus, cardiovascular events and comorbidity leading to worsening of kidney function, that occurred after end of trial in feeder trial
- Record current immunosuppressive medications
- Record treatment with dialysis
- AEs related to trial procedure or IMP in feeder trial will be recorded, see section 9

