2.1 Overview of study procedures

Screening

Screening may be conducted at the earliest at the last visit in the feeder trial and at the latest at Year 1 (one year after start of treatment in the feeder trial +/- the visit window of 2 months).

These assessments and activities are performed:

- Check inclusion and exclusion criteria.
- Sign informed consent.
- Assessment of graft survival. For patients with graft loss after last visit in the feeder trial, date, reason for graft loss, medical history, and root cause will be recorded.
- Record patient survival (if applicable, date and cause of death).
- Pregnancy test (only for Austrian patients due to an exclusion criterion in the protocol version 2.1_AUT_22Nov202 regarding “Lactating or pregnant females”).

At Year 1, Year 2, and Year 3 (End-of-Trial)

The following visit windows applies:

Year 1: (+/- 2 months)

Year 2 and Year 3 (End-of-Trial): (+/- 4 months)

The following activities and assessments will be performed:

- Assessment of graft survival. For patients with graft loss since last visit in the feeder trial or screening (if screening is done at a separate visit), date, reason for graft loss, medical history, and root cause will be recorded.
- Record patient survival (if applicable, date and cause of death).
- Collect information about graft rejection episodes, (classified by Banff 2017 or later). For-cause biopsies together with contemporaneous local DSA analyses, kidney function parameters (P-creatinine, U-albumin/creatinine ratio) and treatments (e.g. plasma exchange and IVIg) will be collected to assess the rejection episodes.
- Record information from standard of care biopsies, if available.
- Sample for S/P-creatinine will be drawn (eGFR will be calculated by the Sponsor)
- Collect urine sample for measurement of albumin/creatinine ratio.
- Sample for HLA antibodies, including DSA, and ADA will be drawn.
- Record comorbidity such as infections, malignancy, diabetes mellitus, cardiovascular events and comorbidity leading to worsening of kidney function, that occurred after end of trial in feeder trial.
- Record current immunosuppressive medications.
- Record treatment with dialysis.
- AEs related to trial procedure or IMP in feeder trial will be recorded.

The study flow chart is displayed in Table 1.

Table1. Flow chart.

Visit (post treatment in feeder trial)	Screening	Year 1	Year 2	Year 3 (EOT)
Visit window	EOT feeder trial to year 1	+/- 2 months	+/- 4 months	+/- 4 months
Assessment				

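### The kidney-function summaries have no graft-status condition, so values taken after graft loss (from a new kidney or on dialysis) can be reported as the treated graft's function

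*SAP*

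**What the plan says.** SAP 4.4.2.3 names three measures (eGFR by the MDRD equation, serum or plasma creatinine, urine albumin/creatinine ratio) and gives one analysis rule: "Variables will be listed by patient and summarized by treatment at Year 1, 2, and 3 after start of treatment in feeder trial". Graft status does not appear in it. SAP 3.1 defines the full analysis set (FAS) as everyone enrolled, allows no other set and bases all outputs on it. SAP 9.1 labels Table 14.2.2 (kidney function) and Table 14.4.1 (creatinine, urine albumin and their ratio) as FAS tables.

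The visit list in SAP 2.1 provides for subjects who have lost the graft: "For patients with graft loss since last visit in the feeder trial or screening (if screening is done at a separate visit"), the date and reason are to be recorded. It also has "Record treatment with dialysis". Protocol 6.1.2 has the same list and, for the same visits, "Sample for S/P-creatinine will be drawn (eGFR will be calculated by the Sponsor"), plus a urine sample. Neither flow chart exempts a subject with a failed graft.

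The one restriction concerns early losses. Protocol 3.1: "Subjects who lose their graft during the feeder trial or in the intermediate time before being able to enter this trial will not continue".

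**The concern.** The protocol treats these measurements as describing the graft. Its synopsis presents creatinine and eGFR as graft-function samples, and section 1.3 gives long-term graft function as the reason for the trial. Graft loss is defined by lasting dialysis, a new transplant or nephrectomy. After any of these, the subject's creatinine no longer measures the graft treated for rejection.

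The two kinds of post-loss value differ. A value after re-transplantation belongs to another kidney, and it normally raises the mean eGFR of the arm that lost the graft. A value on dialysis yields an MDRD number that is not a filtration rate of the graft, though it does fall at the low end. I claim no direction for the urine ratio. If a dialysis patient yields no urine, SAP 4.1.4 leaves the value missing, and the failed graft drops out of that row without comment.

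At stake is whether a reader of Table 14.2.2 can take the arm means as the function of treated grafts.

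**Working it through.** **Does any rule remove a post-loss value?** The plan gives no figure to reproduce here, so the first step is to read the provisions side by side.

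- Protocol 3.1 removes losses before entry. It does not cover losses after entry.
- Protocol 4.5 does not end sampling. A subject who discontinues is called, if possible, to an End-of-Trial visit as set out in 6.1.2, which includes creatinine and urine.
- SAP 4.1.4 deals with missing values, not with a value measured after loss.
- SAP 4.4.1 derives a graft-loss date for the primary endpoint, but SAP 4.4.2.3 does not use it.

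So a measured post-loss value enters the summaries by default.

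**How much weight does one value carry?** Protocol 12.6 anticipates about 20 and 10 patients. One value then carries at least 1/20 = 5% or 1/10 = 10% of an arm mean, and more if fewer are sampled.

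**Illustration.** The formula is the SAP's; every creatinine and the functioning mean are assumptions. For a non-African-American man aged 50, eGFR = 175 × Cr^-1.154 × 50^-0.203 = 79.09 × Cr^-1.154 (Cr in mg/dL, result in mL/min/1.73 m²).

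- Dialysis: Cr 4 gives 15.97, Cr 6 gives 10.00, Cr 10 gives 5.55.
- New kidney: Cr 1.8 gives 40.14, Cr 1.2 gives 64.09, Cr 1.0 gives 79.09.

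Take ten subjects followed: nine functioning grafts at 15, 20, ..., 55 (sum 315) and one lost graft.

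| Summary | Mean | Median | Range |
|---|---|---|---|
| Functioning grafts only, 9 of 10 | 315/9 = 35.0 | 35 | 15 to 55 |
| As written, lost subject on dialysis (10.00) | 325.00/10 = 32.5 | (30+35)/2 = 32.5 | 10.0 to 55 |
| As written, lost subject re-transplanted (64.09) | 379.09/10 = 37.9 | (35+40)/2 = 37.5 | 15 to 64.1 |
| Lost graft ranked lowest | not used | (30+35)/2 = 32.5 | not used |

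With a new kidney, the lost graft raises the median from 35 to 37.5. Counted as a failure, it lowers the median to 32.5.

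**Range for one value.** Shift = (x − 35)/n, where the other n − 1 values average 35:

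- Dialysis, Cr 4 to 10: (15.97−35)/10 = −1.9 to (5.55−35)/10 = −2.9 at n = 10; −1.0 to −1.5 at n = 20.
- New kidney, Cr 1.8 to 1.0: (40.14−35)/10 = +0.5 to (79.09−35)/10 = +4.4 at n = 10; +0.3 to +2.2 at n = 20.

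Mean creatinine moves as well. Against functioning grafts at an assumed 2.0 mg/dL, one dialysis value of 5 to 10 adds (5−2)/10 = 0.30 to (10−2)/10 = 0.80 at n = 10, and half that at n = 20.

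**Is the cut-off date settled?** No. Protocol 7.1 dates a dialysis-defined loss from the start of the period that defines the loss. Protocol 12.3.1 and SAP 4.4.1 date it from the start of the last ongoing period reported. With more than one dialysis period, the second date can be later, and dialysis values between the two dates would still count as functioning.

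**The case against.** **Inference from silence.** A reader might conclude that the SAP instructs that every visit value be summarised regardless of graft status. It does not say so; this follows from the all-enrolled FAS and the lack of any restriction. The supportable claim is that post-loss values can enter, not that they must or did.

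**Keeping failures is defensible.** The endpoint and table titles say kidney function, and a low dialysis eGFR leaves a failed graft near the bottom of its arm. Excluding failures and doing nothing more would flatter the arm that loses more grafts. This stands, and it determines the fix. It does not rescue the new-kidney values, and it does not make the dialysis figure a measure of the graft.

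**Losses can be traced.** With at most 30 subjects, all data are listed by patient, Table 14.2.3 gives absence of graft loss by year, and reasons for loss are tabulated. That stands too. But Table 14.2.2 on its own does not show which values come from failed grafts, and tracing does not correct its means.

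**Exposure might seem to have firm limits.** From "Screening may be conducted at the earliest at the last visit in feeder trial and at the latest at Year 1" and feeder follow-up "up to 180 days after treatment", a reader might place entry between months 6 and 14, leaving at most 14 − 6 = 8 months for a loss before the Year 1 visit. From "The first subject first visit is planned in October 2020, 1 year after first subject was treated in the feeder trial" and the January 2023 termination (SAP 6), a reader might hold that Year 3 values come only from subjects treated by about May 2020 (January 2023 less 32 months). The documents do not support either as a limit. Protocol 4.2 admits subjects who did not complete feeder follow-up, Protocol 4.5 allows early End-of-Trial visits, and the SAP does not say to which year an early End-of-Trial value is assigned.

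**Conclusion.** The point holds in this form: SAP 4.4.2.3 has no graft-status condition, the visits sample subjects whose graft failed after entry without exempting them, and the summaries can therefore attribute new-kidney or dialysis values to the treated graft. Misattribution is clearest after re-transplantation.

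The documents give no count of post-entry losses and no eGFR results, so the actual size cannot be computed. It is nil if no such subject was sampled. The shifts above rest on assumed creatinines, one age and sex, and a functioning mean of 35. They show only that one value can matter in arms of about 10 and 20, in either direction. A reader might infer a bias towards a particular arm; nothing in the documents supports that.

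The endpoint is secondary and descriptive, no test depends on it, and the primary endpoint is unaffected. The change should still be made, because the tables can otherwise misstate what they describe and the correction is small.

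**What to change.** 1. Reconcile the date of a dialysis-defined graft loss between Protocol 7.1 and Protocol 12.3.1 / SAP 4.4.1 before using it as a cut-off.
2. In SAP 4.4.2.3, flag creatinine, eGFR and urine-ratio values dated on or after graft loss. Leave them out of the treated-graft summaries, including any change-from-baseline summary, and label Table 14.2.2 and the creatinine and urine-ratio rows of Table 14.4.1 as functioning grafts.
3. Beside each summary, show number functioning / number followed by arm and visit.
4. Keep the flagged values in Listings 16.2.2 and 16.4.1.
5. Present alongside, as a required output, an eGFR summary that retains failed grafts at a prespecified low value, or a median with failed grafts ranked lowest. Functioning-graft means describe surviving grafts only.

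The cost is a few SAP sentences, one derived flag, one extra row per table and one more summary. The downside is that the functioning-graft means must always be read with the loss counts.
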